- Comprehensive Metabolic Panel with LD, GGT, CRP, direct bilirubin
- Cytokine panel
- CEA, CA 19-9, CA 125
- Circulating Tumor Cell Levels
- Ecotropic murine leukemia virus tests
- Monitoring of adverse events and concomitant medications
- Global clinical assessment
- Quality of life scale
- ECOG and Karnofsky Performance status rating
- Pain scale, if appropriate

5.1.18 Visit 14, Implant 3 / Study Day 60 ± 5 days:

The following data will be obtained:

- Vital signs with weight
- Physical examination with brief neurological exam
- CBC with differential WBC, platelet count
- Coagulation profile (PT, PTT and INR)
- Erythrocyte sedimentation rate
- Comprehensive Metabolic Panel with LD, GGT, CRP, direct bilirubin
- Cytokine panel
- CEA, CA 19-9, CA 125
- Circulating Tumor Cell Levels
- Monitoring of adverse events and concomitant medications

- Global clinical assessment
- Quality of life scale
- ECOG and Karnofsky Performance status rating
- Pain scale, if appropriate

5.1.19 Visit 15, Implant 3 / Study Day 90 ± 5 days:

The following data will be obtained:

- Vital signs with weight
- Physical examination with brief neurological exam
- CBC with differential WBC, platelet count
- Coagulation profile (PT, PTT and INR)
- Erythrocyte sedimentation rate
- Comprehensive Metabolic Panel with LD, GGT, CRP, direct bilirubin
- Cytokine panel
- CEA, CA 19-9, CA 125
- Circulating Tumor Cell Levels
- Ecotropic murine leukemia virus (immunology, PCR) tests
- Monitoring of adverse events and concomitant medications
- Global clinical assessment
- Quality of life scale
- ECOG and Karnofsky Performance status rating
- Pain scale, if appropriate
- MRI if needed
- PET-CT scan of whole body
- Pregnancy test, females of childbearing potential only
- Urinalysis
- CXR
- EKG
- Cellular immune function [T cells, B cells, Antibodies to common bacteria and viruses (diphtheria, tetanus, mumps, rubella), Quantitative IgG subclass determinations, NK cells count (CD16)]
- Murine allergen skin test, including positive and negative controls
- Immunoglobulin Levels (IgA, IgG, IgE, IgM)

Decision to Proceed with Fourth Implantation

All available information from the imaging studies, tumor marker and other laboratory findings, as well as physical examination findings and quality of life measurements from Visit 15 will be reviewed to determine if a subject is cleared

for the proposed anesthesia and fourth implantation of macrobeads. Assuming the subject is cleared, the fourth implantation will proceed as soon as possible.

5.1.20 Visit 16, Implant 4 / Study Day 0:

Beginning 3 months after the third implant, the subject will be scheduled for a fourth implant of the cancer macrobeads at a dosage of 8 macrobeads per kilogram body weight. Assuming that the subject's post-surgical condition is stable (as defined by standard post-operative criteria) and that the subject is taking oral fluids and soft foods at a minimum, the subject will be discharged to home care as soon as medically indicated which may be same day as implantation.

If deemed medically and surgically safe by the operating surgeon, one or more biopsies of tumor mass will be taken during this procedure. Fresh frozen tissue and fixative-treated tissue will be sent to the laboratory for immunohistochemical and gene array analysis to determine any changes in tumor state that may have been the result of exposure to the cancer macrobeads.

5.1.21 Visit 17, Implant 4 / Study Day 14 ± 3 days:

A brief examination including the parameters listed below will be performed. Assuming that the wound examination is satisfactory, all sutures/staples will be removed by the surgeon who performed the laparoscopy or appropriate surrogate. In addition, the Investigator will also examine the subject.

The following data will be obtained:

- Vital signs with weight
- Physical examination with brief neurological exam
- CBC with differential WBC, platelet count
- Coagulation profile (PT, PTT and INR)
- Erythrocyte sedimentation rate
- Comprehensive Metabolic Panel with LD, GGT, CRP, direct bilirubin
- Cytokine panel
- CEA, CA 19-9, CA 125
- Circulating Tumor Cell Levels
- Ecotropic murine leukemia virus tests
- Monitoring of adverse events and concomitant medications
- Global clinical assessment

- Quality of life scale
- ECOG and Karnofsky Performance status rating
- Pain scale, if appropriate

5.1.22 Visit 18, Implant 4 / Study Day 30 ± 5 days:

The following data will be obtained:

- Vital signs with weight
- Physical examination with brief neurological exam
- CBC with differential WBC, platelet count
- Coagulation profile (PT, PTT and INR)
- Erythrocyte sedimentation rate
- Comprehensive Metabolic Panel with LD, GGT, CRP, direct bilirubin
- Cytokine panel
- CEA, CA 19-9, CA 125
- Circulating Tumor Cell Levels
- Ecotropic murine leukemia virus tests
- Monitoring of adverse events and concomitant medications
- Global clinical assessment
- Quality of life scale
- ECOG and Karnofsky Performance status rating
- Pain scale, if appropriate

5.1.23 Visit 19, Implant 4 / Study Day 60 ± 5 days:

The following data will be obtained:

- Vital signs with weight
- Physical examination with brief neurological exam
- CBC with differential WBC, platelet count
- Coagulation profile (PT, PTT and INR)
- Erythrocyte sedimentation rate
- Comprehensive Metabolic Panel with LD, GGT, CRP, direct bilirubin
- Cytokine panel
- CEA, CA 19-9, CA 125
- Circulating Tumor Cell Levels
- Monitoring of adverse events and concomitant medications
- Global clinical assessment
- Quality of life scale
- ECOG and Karnofsky Performance status rating
- Pain scale, if appropriate

5.1.24 Visit 20, Implant 4 / Study Day 90 ± 5 days:

The following data will be obtained:

- Vital signs with weight
- Physical examination with brief neurological exam
- CBC with differential WBC, platelet count
- Coagulation profile (PT, PTT and INR)
- Erythrocyte sedimentation rate
- Comprehensive Metabolic Panel with LD, GGT, CRP, direct bilirubin
- Cytokine panel
- CEA, CA 19-9, CA 125
- Circulating Tumor Cell Levels
- Ecotropic murine leukemia virus (immunology, PCR) tests
- Monitoring of adverse events and concomitant medications
- Global clinical assessment
- Quality of life scale
- ECOG and Karnofsky Performance status rating
- Pain scale, if appropriate
- Urinalysis

5.1.25 Visit 21, Implant 4 / Study Day 120 ± 5 days:

This will be the last formal protocol visit. The following data will be obtained:

- Physical examination with brief neurological exam
- Vital signs with weight
- CBC with differential WBC and platelet count
- Coagulation profile (PT, PTT and INR)
- Erythrocyte sedimentation rate
- Comprehensive Metabolic Panel with LD, GGT, CRP, direct bilirubin
- Cytokine levels
- Ecotropic murine leukemia virus tests
- CEA, CA 19-9, CA 125
- Circulating tumor cells
- Monitoring of adverse events and concomitant medications
- Global clinical assessment
- ECOG and Karnofsky Performance status rating
- Quality of life scale

- ECOG performance scale rating
- MRI as needed, PET-CT scan of whole body
- Pain scale, if appropriate

After Day 120 of the fourth implantation, all examinations and further treatment will be guided by optimal patient care principles and the decisions of the physicians providing overall health care to the subject. It should be noted that all subjects entered into this trial will be followed at appropriate intervals (not less than yearly) for the rest of their lives in accord with USPHS regulations and guidelines for any procedures or treatments involving xenotransplantation.

With regard to the question of whether the macrobeads can or should remain implanted or be removed, the safety data in the laboratory animals and the veterinary patients (cats and dogs) have indicated that the beads are well tolerated for at least one year, four years being the longest that any of the RENCA macrobeads have been followed in vivo to date. Some chronic peritoneal inflammation has been seen with RENCA macrobeads in those animals where the RENCA macrobeads have been in place for more than 3 months, although no clinical evidence of functional problems or signs or symptoms resulting from this reaction has been documented.

In human subjects in the Phase I trial, there has been no evidence that the macrobeads have caused any adverse clinical effects and thus far have been well-tolerated for up to 24 months. This has been true for subjects receiving the 8 macrobeads per kg or 16 macrobeads per kg doses. Four subjects also received a second implant at the 8 macrobeads per kg dose and tolerated that well. Post-mortem results in those subjects consenting to such examination have revealed some fibrinous collections around some of the beads, but no clinically significant peritonitis and no alterations in organ structure or function, specifically bowel function. There have been no requests for or attempts at macrobead removal.

Unfortunately, macrobeads removed at post-mortem examination are not suitable for any testing other than formalin fixation and possibly histology because of the time from death to actual performance of the autopsy. Should any beads be removed in the course of one of the subsequent implantations, they will be sent for histology, MTT testing, inhibition testing, and routine microbiology screening.

The study will continue to follow the subject regardless of macrobead function. Further examinations will be at approximately 6-month intervals for 2 years and then yearly thereafter for the life of the subject. Per PI's discretion, these long-term examinations may include:

- General Physical Examination with Brief neurological Exam;

- Vital signs with weight;
- PET-CT of whole body;
- MRI scans as needed;
- CBC with differential WBC and platelet count;
- Coagulation Panel;
- Erythrocyte sedimentation rate;
- Comprehensive Metabolic Panel with LD, GGT, CRP, direct bilirubin
- CEA, CA 19-9, CA 125;
- Cytokine panel;
- Ecotropic murine leukemia virus tests
- All subjects will be monitored for adverse events and concomitant medications;
- Global clinical assessment;
- Activities of daily living rating;
- Symptoms rating/severity assessment;
- Quality of life scale;
- ECOG and Karnofsky Performance status rating;
- Pain scale, if appropriate;

Should the subject die, and the subject and/or his/her family have consented to it, a postmortem examination will be carried out. Permission for such an examination is requested in the consent form, although the subject's decision cannot be binding on his/her family in the event of the subject's death. The subject is also free to change his/her own decision at any time during or after the study. Samples of tumor tissue (primary and metastatic sites), peritoneum, internal organ serosa and underlying tissue may be taken at any postmortem examination to evaluate tumor state and any inflammatory or connective tissue reaction to the RENCA macrobeads.

5.2 Number of Clinical Sites

One clinical site will be utilized.

5.3 Safety and Tolerability Assessments

All subjects will be monitored for safety at every visit and with telephone follow-ups at regular intervals between visits. At every scheduled study visits, this monitoring will include routine checks of the subject's clinical status, measuring of vital signs, physical examination including a neurological examination, clinical laboratory evaluations including clinical chemistries, hematology, urinalysis, liver functions tests, monitoring of tumor markers, CT/MRI scans as appropriate, and

the monitoring of adverse events, as well as global clinical assessments, quality of life, performance and pain, if any. At unscheduled visits, evaluations will be done at the PI's discretion.

5.4 Medical History

A complete medical history will be collected from each subject. This will include an evaluation of the subject's malignancy, a recording of the results of previous diagnostic tests and therapies. This evaluation will include an assessment of possible therapies that can be used for the management of the malignant condition. The medical/surgical decision to proceed to the first implantation will be made based on the overall clinical assessment. This overall clinical assessment will include an evaluation of the medical history, physical examination, vital signs, EKG, routine blood work, and the absence of evidence of allergic reaction to mouse antigens.

5.5 Physical Examination

All subjects will undergo a complete physical examination including vital signs, with measurement of height and weight.

- Complete physical examination with all vital signs
- Weight
- Global Clinical Assessment

5.6 Clinical Laboratory Parameters

The following clinical laboratory parameters will be tested in all subjects (the schedule is summary in Appendix 2 – Section 9.2):

- EKG
- Biochemical/immune system profile including
- Complete blood count (CBC) with differential WBC and platelet count
- Erythrocyte sedimentation rate
- C-reactive protein
- Biochemical profile as outlined above with amylase, lipase at screening, and thereafter as medically necessary
- Liver function (AST, ALT, LD, alkaline phosphatase, GGT)
- Urinalysis
- Coagulation profile (PT, INR, PTT)

- Hepatitis B, C, E
- HIV
- CEA, CA 19-9, CA 125
- Immunoglobulin levels (IgA, IgG, IgE, IgM)
- Skin testing with murine epithelial antigen preparation, along with positive and negative controls
- Cellular immune function
 - T cells
 - Cytokine production
 - B cells
 - Antibodies to common bacteria and viruses (diphtheria, pertussis, tetanus, mumps, rubella)
 - Quantitative IgG subclass determinations
 - NK cells count (CD16)
- Ecotropic murine leukemia virus (e-MuLV) (PCR-based assay)
- Abdominal/whole body MRI/CT scan with other imaging studies as appropriate for the subject's tumor (primary and metastatic) and condition. Ultrasound examination, if medically indicated, will include views of the hepatic veins and inferior vena cava to be certain that they are free of clots and that there is free peritoneal drainage.

5.7 Appropriateness of Measurements and Assessments

In the evaluation of a therapeutic entity for the treatment of a malignant condition such as advanced pancreatic or colon cancer, the following measurements are appropriate. The response of each subject to the intraperitoneal implantation of RENCA agarose-agarose macrobeads will be measured with respect to:

- primary tumor size
- response: complete, partial, stable disease, progression
- progression as defined in Section 3 of the protocol
- size or number of secondary/metastatic tumors; tumor markers or relevant biochemical parameters such as liver enzymes
- tumor metabolic activity as measured by ¹⁹F-fluorodeoxyglucose uptake (if applicable)
- cellular or humoral immune status
- cytokines
- inflammatory response
- global clinical assessment
- activities of daily living (ADL) rating/performance status
- symptom rating/ severity (including use of pain medications)

- quality of life
- neuropsychological status/cognitive function
- pain rating scale, if appropriate

5.8 Progression of Disease During the Study

In addition to the subject's overall response to the implantation of the RENCA agarose-agarose macrobeads, subjects will be monitored for evidence of progression during the study. Evidence of local or metastatic disease progression will be based on clinical signs and symptoms, imaging studies and biochemical parameters as appropriate after a minimum period of eight weeks after each RENCA macrobead implantation will initiate a formal, documented discussion of the Principal Investigator, subject's attending or primary physician, if any, other consultants if appropriate, and the subject and his/her family regarding consideration of the use of other available standard or experimental therapies. The decision to employ another therapy may be made jointly or by the subject himself/herself.

Where the evidence of such progression is questionable or unclear, review of the subject's condition and laboratory or imaging data (after the minimum period of nine weeks) as defined by the protocol and discussion with the subject and his/her primary physician/consultant(s) will be carried out with careful documentation of the discussions and any decisions or uncertainties. New bone lesions detected on bone scans at the end of the initial 90 days after implantation) may reflect pretreatment disease activity, and may not necessarily constitute disease progression unless confirmed by additional lesions developing subsequently. Hence, subjects will be evaluated for progression based on the following criteria: 1. Tumor progression with PET-CT/MRI assessments after every cycle). 2. Evidence of progression demonstrating the appearance of ≥ 2 new lesions. New lesions detected at the end of the initial implantation period and confirmed confirmation ≥ 6 weeks later. 3. Symptomatic progression (for subjects without measurable disease). Deterioration in ECOG PS of ≥ 2 units compared to baseline attributable to cancer in the opinion of the investigator. 4. Weight loss $\geq 20\%$ (NCI-CTCAE v 3.0, Grade 3) of the initial body weight attributable to cancer in the opinion of the investigator. 5. Other clinical events attributable to the cancer that in the opinion of the investigator require major interventions, such as surgical intervention for pain control. 6. Death from any cause. If in the opinion of the investigator, the subject has symptomatic improvement as measured by improvement in pain scales or narcotic analgesic consumption and there is evidence of bone scan or biochemical progression, he may be continued on treatment at the investigators discretion.

5.9 Rescue Program

During the time period that a subject is participating in this clinical study, the need may arise for additional oncologic therapy. If an alternative or additional therapy other than the macrobeads becomes indicated, because of disease progression, this type of therapy would be considered Rescue Therapy. This would include, for example, chemotherapy, radiation, surgery, or a different experimental protocol. This rescue program would be instituted and would not require the subject to be discontinued from the RENCA macrobead protocol. While undergoing these treatments, the subject will continue to be closely monitored for disease status as well as toxicity, as specified in this protocol. Should the clinical situation develop, the principal investigator and subject, with appropriate consultant input, could restart treatment with the macrobeads. A treatment "holiday" of at least three weeks (for chemotherapy) and four weeks (for radiation) would be required before commencing with this phase II protocol.

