4.3 Selection of Study Population

4.3.1 Inclusion Criteria:

1. Histologically-confirmed adenocarcinoma of the pancreas, colon, or rectum.
2. Radiographic evidence of metastatic cancer of the colon or rectum
3. The subject has pancreatic cancer that is unresectable or already metastatic or colorectal cancer that has failed available treatment modalities.
4. For the pancreas subjects, he/she may be accepted without prior chemotherapy or with multiple therapies that have failed. The colon and rectal cancer subjects must have failed available chemotherapy/targeted regimens. There is no limit to the number of prior chemotherapeutic regimens.
5. The subject must have evidence of progressive disease defined as at least one of the following:
 - a. Progressive measurable disease: using conventional solid tumor criteria
 - b. Increasing tumor markers and/or activity on PET-CT SUV measurement
6. All clinically significant toxic effects (excluding alopecia) of prior surgery, radiotherapy, or hormonal therapy have resolved to \leq Grade 1 based on the NCI-CTCAE v 3.0, with the exception of peripheral neuropathy, which must have resolved to Grade \leq 2.
7. The subject has an Eastern Cooperative Oncology Group performance status (ECOG PS) of 0-2.
8. The subject has adequate hematologic function (minimum requirements: absolute neutrophil count [ANC] \geq 1500/mL, hemoglobin \geq 9 g/dL, and platelets \geq 100,000/mL).
9. The subject has adequate hepatic function (bilirubin \leq 1.5 times the upper limit of normal (ULN)), aspartate transaminase [AST] and alanine transaminase [ALT] \leq 3 times the ULN, or \leq 5 times the ULN, if liver metastases are present).
10. The subject has adequate renal function (creatinine \leq 2.0 mg/dL)
11. The subject has adequate coagulation function (an international normalized ratio [INR] \leq 1.5 and a partial thromboplastin time [PTT] \leq 5 seconds above the ULN [unless on oral anticoagulant therapy]). Subjects receiving full-dose anticoagulation therapy are eligible provided they meet all other criteria, are on a stable dose of oral anticoagulant or low molecular weight heparin (and if on warfarin have a therapeutic INR between 2 and 3).
12. The subject has a life expectancy of 6 weeks.
13. The subject is male or female and at least 18 years of age. For females of childbearing potential, a negative pregnancy test is required.
14. The subject agrees to use contraceptives (barrier method) while on study, if sexually active.

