7 DATA MANAGEMENT AND STATISTICAL ANALYSIS

The critical parameters of this Phase II trial are those related to efficacy. Various markers, such as C-reactive protein, amylase, liver function tests, cell counts, and cytokine levels, will be sampled and analyzed. Given the study design, we will undertake simple population comparisons designed for small samples (non-normal distribution) as well as simple trend analysis for selected parameters. The data from all subjects, including those who withdraw or are withdrawn from the study will be analyzed. All data will be analyzed using SAS software.

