5 ANALYSIS POPULATIONS

All subjects who receive at least one implant will be included in all efficacy and safety evaluations and will be referred to as the Treated Population.

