10.1.3 Change in tumor markers and other biochemical parameters

See [Section 11.1.3](#) below for details on laboratory data collection and reporting. Clinical laboratory parameters will include the tumor markers CEA and CA 19-9. A tumor marker response is defined as a $\geq 20\%$ decrease from baseline in one or both of CEA or CA 19-9.

Other biochemical parameters include:

- Serum enzymes and proteins
- Kidney function (creatinine, blood urea nitrogen (BUN))
- C-reactive protein
- Hematology (leukocytes, hemoglobin, differential, platelets, erythrocyte sedimentation rate (ESR))
- Cytokines
- Cellular and humoral immunity status (observed values will be clinically reviewed to determine presence / absence of each antibody, etc.)
- CA125 is included as part of the assessment of inflammatory response to macrobead placement.

Along with listings and summaries, graphical displays of individual subject observed values over time will be produced for tumor markers, CA125, C-reactive protein, and ESR.

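### Tumor-marker and imaging responses that appear after on-study rescue therapy count as macrobead responses, because no response definition excludes them

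*Protocol*

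**What the plan says.** - **Rescue.** Protocol 5.9 covers other therapy that becomes indicated because of progression: "This would include, for example, chemotherapy, radiation, surgery, or a different experimental protocol". Participation does not end: "This rescue program would be instituted and would not require the subject to be discontinued from the RENCA macrobead protocol". Meanwhile "the subject will continue to be closely monitored for disease status as well as toxicity, as specified in this protocol". The investigator and subject "could restart treatment with the macrobeads" after a break of at least three weeks (chemotherapy) or four weeks (radiation).
- **Who is analysed.** SAP 5: "All subjects who receive at least one implant will be included in all efficacy and safety evaluations". Protocol 7: "The data from all subjects, including those who withdraw or are withdrawn from the study will be analyzed".
- **What counts as response.** SAP 10.1.3 defines a marker response as a 20% or greater "decrease from baseline in one or both of CEA or CA 19-9". Protocol 3.2.1, the pancreatic primary objective, builds the Response Rate from imaging, markers, quality of life, clinical rating and LDH, at times from 2 weeks to 12 months or beyond. Protocol 7.2 rates every subject before each implantation, or on leaving the study, against one baseline taken before the first implant. None of the three mentions other therapy.
- **Who may enter.** Protocol 4.3.1, criterion 4: "For the pancreas subjects, he/she may be accepted without prior chemotherapy or with multiple therapies that have failed".

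**The concern.** The trial has one arm and no concurrent control, so a response caused by another treatment cannot show up as a difference between groups. It enters the macrobead rate directly. The exposure is plainest in pancreatic subjects who enter without prior chemotherapy, because rescue may be their first chemotherapy.

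The estimates are the product of this trial. Appendix 3 (section 1) and SAP 3.2 say the aim is to estimate parameters for planning later trials, and Protocol 7.1 says the pancreatic data will be used to plan a controlled Phase IIb study. A response rate that mixes macrobead and rescue effects would carry into that planning.

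**Working it through.** **Step 1. Is there any rule for post-rescue efficacy data?**

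- SAP 10.1.1 censors only subjects alive at the time of analysis. There is no censoring at new therapy.
- SAP 6.4.3 takes the last valid value in each window, and validity is not tied to rescue.
- SAP 9 lists and summarises concomitant medications but links them to no efficacy rule.
- SAP 3.2 foresees that patients may begin new therapy, yet no analysis section deals with it.
- The sub-analyses in Appendix 3 (section 4) are optional and are not defined by rescue.
- The three- or four-week break in Protocol 5.9 governs restarting macrobeads. It is not a data rule.

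No sentence says outright that post-rescue data count. They count by default.

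**Step 2. Where can post-rescue values enter?**

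- *Early visits.* Protocol 5.8 sets a minimum of eight weeks (8 × 7 = 56 days) after each implant before progression prompts discussion of other therapy. Days 14 and 30 of a first cycle are therefore largely free of rescue.
- *Days 60 and 90.* The SAP 6.4.4 windows are days 53–67 and 83–97. Some values can follow rescue.
- *After day 97.* Values are unscheduled, so they are listed but not analysed. The exception in the window table is days 113–127 after implant 4 (end of study).
- *After re-implantation.* SAP 6.4.1.2 resets baseline at each implant, so an earlier rescue effect is already in the new baseline and the most-recent-implant comparison is largely unaffected. Imaging, rating scales and laboratory values are also reported against the first implant (SAP 10.1.2, 10.1.4, 11.1.3), and there the rescue effect remains.
- *Protocol 7.2 ratings.* For a subject re-implanted after rescue, the rating is made after the rescue course, before the new beads are placed, and against the pre-first-implant baseline. This is the clearest route.

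**Step 3. The plan's precision, for scale.** Appendix 3 (section 9) gives at most 22 points (colorectal) and 31 points (pancreatic) at a 50% rate. With half-width = 1.96 × √(0.25/n):

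- n = 20: 21.9 points; n = 10: 31.0 points. Both stated figures reproduce at the original sample sizes.
- At the current 40 pancreatic and 74 − 40 = 34 colorectal subjects: 15.5 and 16.8 points.

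**Step 4. Size under assumed values.** Let f be the share of subjects with an analysed post-rescue assessment, r the share of those who meet the response definition because of rescue, and p the true macrobead response rate. If these are independent, bias = f × r × (1 − p). The documents give none of the three, so all values below are assumptions, applied to 40 pancreatic subjects.

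| f | r | p | Bias (points) | Extra responders |
|---|---|---|---|---|
| 10% | 10% | 0 | 1 | 0.4 |
| 30% | 20% | 0 | 6 | 2.4 |
| 50% | 40% | 0 | 20 | 8 |
| 10% | 10% | 10% | 0.9 | 0.4 |
| 50% | 40% | 10% | 18 | 7.2 |

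The top of the range exceeds the 15.5-point half-width; the middle and lower values do not.

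**The case against.** The case on the other side has weight. Analysing all implanted subjects regardless of compliance is stated policy, all analyses are exploratory, and the windows and baseline reset in Step 2 keep much post-rescue data out. Whole-body PET-CT is scheduled at Day 90, so rescue prompted by that scan mostly yields values outside any analysed window unless the subject is re-implanted. The SAP also says it supersedes the protocol's statistics and has modified response rate, and the only response it defines is for markers.

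These points narrow the exposure but do not remove it. The SAP marker definition has the same gap, and Amendment 11, which is later than the amendment the SAP cites, keeps Response Rate as the pancreatic primary objective.

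Three stronger readings are tempting and are not supported:

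- *A reader might infer that every efficacy measure is biased upward.* Chemotherapy or surgery could worsen quality of life, pain or ECOG, so the direction there is unknown.
- *A reader might assume that 30% of 40 pancreatic subjects are rescued (12) and 30–50% of those have a 20% marker fall on rescue (3.6–6), giving 9–15 points.* That counts falls from the start of rescue, whereas the SAP requires a fall from baseline. Rescue follows progression, so markers may already be raised. From the 50% rise that Protocol 3.2.2 lists as one progression event, reaching 0.8 of baseline needs a fall of 1 − 0.8/1.5 = 47%. The figure also assumes that every rescued subject has an analysed value.
- *A reader might conclude that post-rescue values should be dropped from all summaries.* Rescue is triggered by progression and missing values are not imputed (SAP 6.3). Dropping them would remove progressors from later means and could itself flatter the macrobeads.

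**Conclusion.** The point holds in limited form. As written, a marker fall of 20% or more from baseline, or an imaging response, that occurs after rescue counts as a macrobead response. The bias is upward for these two outcomes. It arises mainly in some Day 60 and Day 90 values, the end-of-study window after implant 4, visits after re-implantation judged against the first-implant baseline, and the Protocol 7.2 ratings.

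The size cannot be computed from the documents. The range of about 1 to 20 percentage points rests wholly on assumed values of f and r with no true macrobead response. The consequence is a distorted planning estimate rather than an inflated type I error, since no confirmatory test is planned. It should be corrected before analysis.

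**What to change.** - **Response.** In SAP 10.1.3, and wherever the Protocol 3.2.1 or 7.2 response is tabulated, state that an assessment after the start of any other anticancer therapy does not count toward response. A subject with no response before that date is a non-responder and stays in the denominator. Show the all-data response rate as supportive.
- **Continuous changes from baseline.** Keep the all-data summaries and flag post-rescue values. Show a version without them as a sensitivity analysis only, for the reason given above.
- **Reporting.** Give the number of subjects rescued and the time to rescue.
- **Data capture.** Confirm that the CRF records start dates of rescue radiation and surgery. SAP 9 covers medications, but the listings in SAP 16.1 show none for on-study radiation or procedures.
- **Unchanged.** Deaths after rescue still count in all survival analyses, and no change to the clinical rescue rule is suggested.

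The cost is SAP wording, possibly one CRF date field, and somewhat lower response figures.
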